Appendix 6. Sample Storage and Destruction

Any blood sample collected according to the Schedule of Activities (see [Table 2-1](#), [Table 2-2](#), [Table 2-3](#), [Table 2-4](#), [Table 2-5](#), [Table 2-6](#), [Table 2-7](#), and [Table 2-8](#)) can be analyzed for any of the tests outlined in the protocol and for any tests necessary to minimize risks to study subjects. This includes testing to ensure analytical methods produce reliable and valid data throughout the course of the study. This can also include, but is not limited to, investigation of unexpected results, incurred sample reanalysis, and analyses for method transfer and comparability.

All samples and associated results will be coded prior to being shipped from the site for analysis or storage. Samples will be tracked using a unique identifier that is assigned to the samples for the study. Results are stored in a secure database to ensure confidentiality.

If informed consent is provided by the subject, Amgen can do additional testing on remaining samples (ie, residual and back-up) to investigate and better understand the dose response and/or prediction of response to efavaleukin alfa, and characterize aspects of the molecule (eg, mechanism of action/target, metabolites). Results from this analysis are to be documented and maintained, but are not necessarily reported as part of this study. Samples can be retained for up to 20 years.

Since the evaluations are not expected to benefit the subject directly or to alter the treatment course, the results of pharmacogenetic, [biomarker development,] or other exploratory studies are not placed in the subject's medical record and are not to be made available to the subject, members of the family, the personal physician, or other third parties, except as specified in the informed consent.

The subject retains the right to request that the sample material be destroyed by contacting the investigator. Following the request from the subject, the investigator is to provide the sponsor with the required study and subject number so that any remaining [sample types (eg, blood, tumor)] samples and any other components from the cells can be located and destroyed. Samples will be destroyed once all protocol-defined procedures are completed. However, information collected from samples prior to the request for destruction, will be retained by Amgen.

The sponsor is the exclusive owner of any data, discoveries, or derivative materials from the sample materials and is responsible for the destruction of the sample(s) at the request of the subject through the investigator, at the end of the storage period, or as

appropriate (eg, the scientific rationale for experimentation with a certain sample type no longer justifies keeping the sample). If a commercial product is developed from this research project, the sponsor owns the commercial product. The subject has no commercial rights to such product and has no commercial rights to the data, information, discoveries, or derivative materials gained or produced from the sample. See [Appendix 3](#) for subject confidentiality.

Appendix 7. Hepatotoxicity Stopping Rules: Suggested Actions and Follow-up Assessments and Study Treatment Rechallenge Guidelines

Subjects with abnormal hepatic laboratory values (ie, alkaline phosphatase [ALP], aspartate aminotransferase [AST], alanine aminotransferase [ALT], total bilirubin [TBL]) and/or international normalized ratio (INR) and/or signs/symptoms of hepatitis (as described below) may meet the criteria for withholding or permanent discontinuation of Amgen investigational product or other protocol-required therapies, as specified in the *Guidance for Industry Drug-Induced Liver Injury: Premarketing Clinical Evaluation, July 2009*.

Criteria for Withholding and/or Permanent Discontinuation of Amgen Investigational Product and Other Protocol-required Therapies Due to Potential Hepatotoxicity

The following stopping and/or withholding rules apply to subjects for whom another cause of their changes in liver biomarkers (TBL, INR and transaminases) has not been identified.

Important alternative causes for elevated AST/ALT and/or TBL values include, but are not limited to:

- GVHD
- Hepatobiliary tract disease
- Viral hepatitis (eg, hepatitis A/B/C/D/E, Epstein-Barr Virus, cytomegalovirus, herpes simplex virus, varicella, and parvovirus)
- Protozoal infections (eg, toxoplasmosis, schistosomiasis)
- Right sided heart failure, hypotension or any cause of hypoxia to the liver causing ischemia
- Exposure to hepatotoxic agents/drugs or hepatotoxins, including herbal and dietary supplements, plants and mushrooms
- Heritable disorders causing impaired glucuronidation (eg, Gilbert's syndrome, Crigler-Najjar syndrome) and drugs that inhibit bilirubin glucuronidation (eg, indinavir, atazanavir)
- Alpha-one antitrypsin deficiency
- Alcoholic hepatitis
- Autoimmune hepatitis
- Wilson's disease and hemochromatosis
- Nonalcoholic fatty liver disease including steatohepatitis (NASH)
- Non-hepatic causes (eg, rhabdomyolysis, hemolysis)

If investigational product(s) is/are withheld, the subject is to be followed for possible DILI according to recommendations in the last section of this appendix.

Rechallenge may be considered if an alternative cause for impaired liver tests (ALT, AST, ALP) and/or elevated TBL, is discovered and the laboratory abnormalities resolve to normal or baseline (see next section in this appendix).

Table 12-2. Conditions for Withholding and/or Permanent Discontinuation of Amgen Investigational Product and Other Protocol-required Therapies Due to Potential Hepatotoxicity

Analyte	Temporary Withholding	Permanent Discontinuation
TBL	> 3x ULN at any time	> 2x ULN
OR		
INR	--	> 1.5x ULN (for subjects not on anticoagulation therapy)
AND		
AST/ALT	> 8x ULN at any time > 5x ULN but < 8x ULN for \geq 2 weeks > 5x ULN but < 8x ULN and unable to adhere to enhanced monitoring schedule > 3x ULN with clinical signs or symptoms that are consistent with hepatitis (such as right upper quadrant pain/tenderness, fever, nausea, vomiting, and jaundice)	In the presence of no important alternative causes for elevated AST/ALT and/or TBL values > 3x ULN (when baseline was < ULN)
OR		
ALP	> 8x ULN at any time	--

ALP = alkaline phosphatase; ALT = alanine aminotransferase; AST = aspartate aminotransferase; INR = international normalized ratio; TBL = total bilirubin; ULN = upper limit of normal

Criteria for Rechallenge of Amgen Investigational Product and Other Protocol-required Therapies After Potential Hepatotoxicity

The decision to rechallenge the subject is to be discussed and agreed upon unanimously by the subject, investigator, and Amgen.

If signs or symptoms recur with rechallenge, then efavaleukin alfa is to be permanently discontinued. Subjects who clearly meet the criteria for permanent discontinuation (as described in [Table 12-2](#)) are never to be rechallenged.

Drug-induced Liver Injury Reporting and Additional Assessments

Reporting

To facilitate appropriate monitoring for signals of DILI, cases of concurrent AST or ALT and TBL and/or INR elevation, according to the criteria specified in the above, require the following:

- The event is to be reported to Amgen as a serious adverse event within 24 hours of discovery or notification of the event (ie, before additional etiologic investigations have been concluded)
- The appropriate CRF (eg, Event CRF) that captures information necessary to facilitate the evaluation of treatment-emergent liver abnormalities is to be completed and sent to Amgen

Other events of hepatotoxicity and potential DILI are to be reported as serious adverse events if they meet the criteria for a serious adverse event defined in [Appendix 4](#).

Additional Clinical Assessments and Observation

All subjects in whom investigational product(s) or protocol-required therapies is/are withheld (either permanently or conditionally) due to potential DILI as specified in [Table 12-2](#) or who experience AST or ALT elevations $> 3 \times$ upper limit of normal (ULN) or 2-fold increases above baseline values for subjects with elevated values before drug are to undergo a period of “close observation” until abnormalities return to normal or to the subject’s baseline levels.

Additional laboratory assessments for hepatotoxicity monitoring will be performed locally.

Assessments that are to be performed during this period include:

- Repeat AST, ALT, ALP, bilirubin (total and direct), and INR within 24 hours
- In cases of TBL $> 2 \times$ ULN or INR > 1.5 , retesting of liver tests, BIL (total and direct), and INR is to be performed every 24 hours until laboratory abnormalities improve

Testing frequency of the above laboratory tests may decrease if the abnormalities stabilize or the investigational product(s) or protocol-required therapies has/have been discontinued AND the subject is asymptomatic.

Initiate investigation of alternative causes for elevated AST or ALT and/or elevated TBL.

The following are to be considered depending on the clinical situation:

- Complete blood count (CBC) with differential to assess for eosinophilia
- Serum total immunoglobulin IgG, anti-nuclear antibody (ANA), anti smooth muscle antibody, and liver kidney microsomal antibody - 1 (LKM1) to assess for autoimmune hepatitis

- Serum acetaminophen (paracetamol) levels
- A more detailed history of:
 - Prior and/or concurrent diseases or illness
 - Exposure to environmental and/or industrial chemical agents
 - Symptoms (if applicable) including right upper quadrant pain, hypersensitivity-type reactions, fatigue, nausea, vomiting and fever
 - Prior and/or concurrent use of alcohol, recreational drugs and special diets
 - Concomitant use of medications (including non-prescription medicines and herbal and dietary supplements), plants, and mushrooms
- Viral serologies
- Creatine phosphokinase (CPK), haptoglobin, lactate dehydrogenase (LDH), and peripheral blood smear
- Appropriate liver imaging if clinically indicated
- Appropriate blood sampling for pharmacokinetic analysis if this has not already been collected
- Hepatology consult (liver biopsy may be considered in consultation with a hepatologist)

Follow the subject and the laboratory tests (ALT, AST, TBL, INR) until all laboratory abnormalities return to baseline or normal or considered stable by the investigator. The "close observation period" is to continue for a minimum of 4 weeks after discontinuation of all investigational product(s) and protocol-required therapies.

The potential DILI event and additional information such as medical history, concomitant medications and laboratory results must be captured in the corresponding CRFs.

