110 Subject must have adequate hepatic function, defined below, unless the treating physician documents the abnormal LFTs as consistent with hepatic cGVHD:

- total bilirubin $<$ 2.0 mg/dL (34.2 μ mol/L) [elevated values due to Gilbert's Syndrome or of non-hepatic origin are excluded].
- aspartate transaminase [AST; SGOT]/Alanine transaminase [ALT; SGPT] \leq 2x upper limit of normal (ULN).
- If LFT abnormalities are deemed consistent with hepatic cGVHD by the investigator, a liver biopsy will not be mandated.

111 Subject must have adequate pulmonary function defined as: forced expiratory volume in 1 second (FEV1) \geq 50% or hemoglobin-adjusted diffusion capacity for

carbon monoxide (D_{LCO} Hb) \geq 40% of predicted, unless pulmonary dysfunction is deemed to be due to cGVHD.

112 Subject must have adequate renal function defined as: a calculated glomerular filtration rate of > 50 mL/min/1.73 m² using the MDRD formula.

113 Subject must have adequate cardiac function defined as: no history within 6 months prior to screening of myocardial infarction, unstable angina, New York Heart Associate Class III or IV heart failure, or stroke. No findings on the screening electrocardiogram (ECG) that in the opinion of the investigator requires further cardiovascular evaluation, including severe uncontrolled ventricular arrhythmias, electrocardiographic evidence of acute ischemia or active conduction system abnormalities.

114 Subject must have adequate bone marrow function indicated by ANC $> 1.00 \times 10^9/L$ and platelets $> 50 \times 10^9/L$ without growth factors or transfusions within the 4 weeks prior to starting efavaleukin alfa.

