### **9.6.3            Laboratory Test Results**

#### **9.6.3.1        Chemistry and Hematology**

The analyses of safety laboratory endpoints will include summary statistics of baseline, post-baseline lab values at all the time points, change from baseline to post-baseline, post-baseline maximum/minimum and change from baseline to post-baseline maximum/minimum by dose level.

Shifts tables indicating the change between the baseline and the worst post dose CTCAE grades based on CTCAE version 4.03 or later will be provided for selected laboratory parameters of interest. Subject incidence of worst post-baseline eosinophils counts by the laboratory normal range will be provided.

**Chemistry and hematology laboratory tests performed by local laboratories will be included in the analyses where applicable in cases where central laboratory values were not obtainable (i.e. due to Covid restrictions).**

A listing of subjects identified as potential Hy's law cases (ALT or AST of >3xULN associated with total bilirubin > 2xULN and ALP <2xULN at a visit) will be provided with relevant laboratory tests included in the listing.

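### Table 12-2 directs no hold or stop in a narrow band of unexplained liver signals when baseline AST/ALT is at or above ULN (cheap improvement, low expected impact)

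*Protocol*

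**What the plan says.** **Entry.** Protocol 6.1, criterion 110, reads: "Subject must have adequate hepatic function, defined below, unless the treating physician documents the abnormal LFTs as consistent with hepatic cGVHD". The AST/ALT limit is at most "2x upper limit of normal (ULN"), and the hepatic cGVHD exception carries no upper limit.

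**Scope of the liver rules.** In Protocol Appendix 7 the "rules apply to subjects for whom another cause of their changes in liver biomarkers (TBL, INR and transaminases) has not been identified". GVHD is on the list of alternative causes.

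**Permanent discontinuation (Table 12-2).** TBL > 2x ULN, or INR > 1.5x ULN off anticoagulation, must occur together with AST/ALT "> 3x ULN (when baseline was < ULN") and no important alternative cause. There is no entry for a raised baseline, and the ALP cell is blank.

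**Temporary withholding (Table 12-2).** The triggers carry no baseline condition:
- TBL > 3x ULN
- AST/ALT > 8x ULN
- AST/ALT > 5x to < 8x ULN for at least 2 weeks, or where enhanced monitoring cannot be kept up
- AST/ALT > 3x ULN with hepatitis signs or symptoms
- ALP > 8x ULN

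INR has no withholding trigger.

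**Monitoring.** Close observation starts at AST/ALT > 3x ULN, or at "2-fold increases above baseline values for subjects with elevated values before drug". Once INR exceeds 1.5 or TBL exceeds 2x ULN, a further rule applies: "retesting of liver tests, BIL (total and direct), and INR is to be performed every 24 hours until laboratory abnormalities improve".

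**Analysis.** SAP 9.6.3.1 lists potential Hy's law cases as "ALT or AST of >3xULN associated with total bilirubin > 2xULN and ALP <2xULN at a visit", with no baseline restriction.

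**The concern.** The protocol admits subjects with raised transaminases, but its only permanent-stop AST/ALT condition excludes them. If the withholding lines do not cover the same values, two subjects with identical unexplained on-study results are treated differently: one must stop for good, and for the other the table directs nothing. The values are a combined rise in transaminases with bilirubin or INR. Part of that range is what the SAP lists as potential Hy's law. At stake is further weekly or biweekly dosing through a liver signal, unless the investigator or sponsor chooses to intervene. A related effect is that Appendix 7 bars rechallenge for good only in subjects who meet the permanent criteria, so that bar does not reach the raised-baseline group.

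**Working it through.** The plan gives no figure to reproduce, so the check is one of rule coverage. Each withholding line is read as a trigger on its own, which is the most protective reading.

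**Step 1: one case, two baselines.** ALT 4x ULN, TBL 2.5x ULN, INR 1.0, ALP 1x ULN, one week's duration, monitoring kept up, no symptoms, no other cause.

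| Table 12-2 line | Baseline 0.8x ULN | Baseline 1.5x ULN |
|---|---|---|
| Permanent: TBL > 2x or INR > 1.5x, and AST/ALT > 3x with baseline < ULN | Met (2.5 > 2, 4 > 3, 0.8 < 1) | Not met (1.5 is not < 1) |
| Hold: TBL > 3x | No (2.5) | No (2.5) |
| Hold: AST/ALT > 8x | No (4) | No (4) |
| Hold: AST/ALT > 5x to < 8x, prolonged or unmonitored | No (4) | No (4) |
| Hold: AST/ALT > 3x with symptoms | No symptoms | No symptoms |
| Hold: ALP > 8x | No (1) | No (1) |
| **Result** | **Permanent stop** | **No drug action directed** |

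The INR branch behaves the same way. ALT 4x, TBL 1.0x and INR 2.5x ULN off anticoagulation gives a permanent stop at the normal baseline and no directed action at the raised one, because INR has no withholding entry.

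**Step 2: edges of the band.** For a baseline at or above ULN, with no other cause, no symptoms and ALP not above 8x ULN, no hold or stop is directed when both of these hold:
- AST/ALT is > 3x to 5x ULN (no time limit, since the 2-week line starts above 5x), or > 5x to < 8x ULN for under 2 weeks with monitoring kept up.
- TBL is > 2x to 3x ULN, or INR is > 1.5x ULN with TBL not above 3x ULN.

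**Step 3: coverage with duration and symptoms varied.** The inputs are six AST/ALT values (3.5, 4.9, 6, 7.9, 8.0 and 9x ULN), four TBL/INR pairs (2.5 and 1; 3.5 and 1; 1 and 1.6; 1 and 3) and three settings (short without symptoms; 2 weeks or more without symptoms; short with symptoms). That gives 6 x 4 x 3 = 72 combinations, all with AST/ALT > 3x ULN plus TBL > 2x ULN or INR > 1.5.
- Baseline 0.8x ULN: permanent stop in 72 of 72.
- Baseline 1.0x, 1.5x or 2.0x ULN: permanent stop in 0, temporary hold in 48, no directed action in 24.

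The 24 are 6 + 6 + 3 + 3 + 6 + 0 across the six AST/ALT values in order. The 6 at exactly 8.0x arise only because both neighbouring lines use strict inequalities; without them the count is 18. If the AND in the table also ties the TBL and AST/ALT rows in the withholding column, the 24 becomes 62 at a 1.5x baseline. These are counts of rule combinations and say nothing about how often they occur in patients.

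**Step 4: size.** SAP 3.2 plans about 30 escalation subjects. SAP 3.1 cancels the expansion cohort and reports that cohort 5 enrollment was discontinued. Neither document gives the share with baseline AST/ALT at or above ULN or the rate of unexplained combined rises, so the number affected cannot be computed.

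**The case against.** The strongest reply is that raised baselines are handled by other means. Close observation covers them by name, tests are repeated within 24 hours and then daily while TBL or INR stays high, and a search for causes is required. Section 8.1 allows removal for an adverse event or by sponsor decision. Jaundice, nausea or fever consistent with hepatitis brings a hold from AST/ALT > 3x ULN. Dosing is only weekly or biweekly, given by site staff. Limiting a permanent, no-rechallenge stop to normal baselines is also defensible: a move from 2x to 3.1x ULN is only a 1.55-fold rise.

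Most of this stands and keeps the point small. It does not close the gap, because observation, reporting and discretion are not a hold. Retesting may also be spaced out once values stabilise in an asymptomatic subject.

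A reader might infer three stronger claims that the documents do not support:
- *That 24-hour liver-injury reporting fails for this group.* The report is due "before additional etiologic investigations have been concluded", so it more naturally follows the analyte thresholds.
- *That the SAP requires a stop at Hy's law values.* The listing is an analysis output and sets no stopping rule. It also omits the INR branch and cases with ALP at or above 2x ULN.
- *That the baseline qualifier should be deleted, or a permanent stop added at a set multiple of baseline.* The documents give no multiple for a permanent stop, and deletion would permanently stop the 1.55-fold case if TBL or INR also qualified.

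**Conclusion.** The point holds as a minor one: a cheap improvement with low expected impact. On the readable text, raised-baseline subjects in the band of Step 2 have no directed hold or stop, while normal-baseline subjects at the same values must stop permanently. This does not show that the permanent-stop rule is wrong or that these subjects go unmonitored.

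The size is small but cannot be quantified. The group is a subset of about 30 escalation subjects and needs several conditions at once. SAP sections 1 and 3.1 state that the study is terminated early, so any benefit reaches only subjects still dosing, and the documents do not say whether there are any.

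The conclusion rests on these readings:
- Each withholding line stands alone; the other reading widens the gap.
- Both AST and ALT are at or above ULN at baseline. A subject with one normal enzyme could arguably qualify for the permanent stop through that enzyme.
- The end of Protocol 7.4.3 and all of 7.4.2.1.2 are not readable in the public text and might contain a relevant instruction. Appendix 7 also cites an external guidance on drug-induced liver injury that was not available here.

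**What to change.** Add one line to the Temporary Withholding column of Table 12-2: *AST/ALT > 3x ULN with TBL > 2x ULN, or with INR > 1.5x ULN if not on anticoagulation, when baseline AST/ALT was at or above ULN and no important alternative cause has been identified.* Restart would follow only the existing rechallenge rules of Appendix 7. Every combination in the band of Step 2 has AST/ALT > 3x ULN plus one of the two companion conditions, so the line covers the whole band at any raised baseline.

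Leave to the sponsor's hepatic safety function whether such cases should be stopped permanently, and at what multiple of baseline.

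The cost is one table line, with no new tests, visits, staff or subjects. As a protocol text change it needs IRB/IEC submission and, where required, approval (Appendix 3), and it can travel with another amendment. The downside is possibly a few more withheld doses while a cause is sought. Because the existing rules consider rechallenge only once an alternative cause is found and values have resolved, a hold with no cause found would continue.

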Appendix 8. NIH Defined Diagnostic or Distinctive Features of Chronic GVHD

Organ or site	Diagnostic (sufficient to Establish the Diagnosis of Chronic GVHD)	Distinctive ^a (Seen in Chronic GVHD, but insufficient Alone to Establish a Diagnosis of Chronic GVHD)	Other Features or Unclassified Entities ^b	Common ^c (Seen with Both Acute and Chronic GVHD)
Skin	Poikiloderma Lichen planus-like features Sclerotic features Morphea-like features Lichen sclerosus-like features	Depigmentation Papulosquamous lesions	Sweat impairment Ichthyosis Keratosis pilaris Hypopigmentation Hyperpigmentation	Erythema Maculopapular rash Pruritus
Nails	-	Dystrophy Longitudinal ridging, splitting, or brittle features Onycholysis Pterygium unguis Nail loss (usually symmetric; affects most nails) ^b	-	-
Scalp and body hair	-	New onset of scarring or nonscarring scalp alopecia (after recovery from chemoradiotherapy) Loss of body hair Scaling	Thinning scalp hair, typically patchy, coarse, or dull (not explained by endocrine or other causes) Premature gray hair	-
Mouth	Lichen-type features	Xerostomia Mucocele Mucosal atrophy Ulcers Pseudomembranes	-	Gingivitis Mucositis Erythema Pain

Page 1 of 3

Organ or site	Diagnostic (sufficient to Establish the Diagnosis of Chronic GVHD)	Distinctive ^a (Seen in Chronic GVHD, but insufficient Alone to Establish a Diagnosis of Chronic GVHD)	Other Features or Unclassified Entities ^b	Common ^c (Seen with Both Acute and Chronic GVHD)
Eyes	-	New onset dry, gritty, or painful eyes Cicatricial conjunctivitis Keratoconjunctivitis sicca Confluent areas of punctate keratopathy	Photophobia Periorbital hyperpigmentation Blepharitis (erythema of the eyelids with edema)	-
Genitalia	Lichen planus-like features Lichen sclerosus-like features Females Vaginal scarring or clitoral/labial agglutination Males Phimosis or urethral/meatus scarring or stenosis	Erosions Fissures Ulcers	-	-
GI Tract	Esophageal web Strictures or stenosis in the upper to mid third of the esophagus	-	Exocrine pancreatic insufficiency	Anorexia Nausea Vomiting Diarrhea Weight loss Failure to thrive (infants and children)
Liver	-	-	-	Total bilirubin, alkaline phosphatase > 2 x ULN ALT or AST > 2 x ULN

Organ or site	Diagnostic (sufficient to Establish the Diagnosis of Chronic GVHD)	Distinctive ^a (Seen in Chronic GVHD, but insufficient Alone to Establish a Diagnosis of Chronic GVHD)	Other Features or Unclassified Entities ^b	Common ^c (Seen with Both Acute and Chronic GVHD)
Lung	Bronchiolitis obliterans diagnosed with lung biopsy Bronchiolans obliterans syndrome (BOS) ^d	Air trapping and bronchiectasis on chest CT	Cryptogenic organizing pneumonia (COP) ^e Restrictive lung disease ^e	
Muscles, fascia, joints	Fasciitis Joint stiffness or contractures secondary to sclerosis	Myositis or polymyositis ^f	Edema Muscle cramps Arthralgia or arthritis	-
Hematopoietic and immune	-	-	Thrombocytopenia Eosinophilia Lymphopenia Hypo- or hyper-gammaglobulinemia Autoantibodies (AIHA and ITP) Raynaud's phenomenon	-
Other	-	-	Pericardial or pleural effusions Ascites Peripheral neuropathy Nephrotic syndrome Myasthenia gravis Cardiac conduction abnormality or cardiomyopathy	-

Page 3 of 3

^a In all cases, infection, drug effect, malignancy, or other causes must be excluded.

^b Can be acknowledged as part of the chronic GVHD manifestations if diagnosis is confirmed.

^c Common refers to shared features by both acute and chronic GVHD.

^d BOS can be diagnostic for lung chronic GVHD only, if distinctive sign or symptom present in another organ.

^e Pulmonary entities under investigation or unclassified.

^f Diagnosis of chronic GVHD requires biopsy.

Source: Jagasia et al, 2015

